8.4.3. Classification of Severity of Adverse Event

The severity of AEs will be categorized as shown below, based on common terminology criteria for adverse events (CTCAE) Version 5.0 criteria.

Table 9. Categorization of Severity of Adverse Events

| | |
|-------------------------------------|---|
| Mild | The event is minor and does not cause significant discomfort to subject or change in activities of daily living (ADL); participant is aware of symptoms, but symptoms are easily tolerated. |
| Moderate | The event is an inconvenience or concern to the subject and causes interference with ADL, but the participant is able to continue with ADL. |
| Severe | The event significantly interferes with ADL and the subject is incapacitated and/or unable to continue with ADL. |
| Potentially life threatening | An event/reaction in which the subject was at risk of death at the time of the event/reaction; it does not refer to an event/reaction, which hypothetically might have caused death if it were more severe. |

8.4.3.1. Relationship to Study Drug

The investigator will make a determination of the relationship of the AE to the study drug using a 4-category system (not related, possible, probable, definite), as shown below, based on common terminology criteria for adverse events (CTCAE) Version 5.0 criteria.

Table 10. Categorization for Determining Relationship of AEs to Study Treatment

| | |
|--------------------|---|
| Not related | An AE that does not follow a reasonable temporal sequence from administration of the drug and that can be reasonably explained by other factors, including underlying disease, complications, concomitant drugs, or concurrent treatment. |
| Possible | An AE that follows a reasonable temporal sequence from the administration of the drug (including the course after withdrawal of the drug) and that cannot be excluded as being possibly caused by the drug (e.g., existence of similar reports attributed to the drug and/or its analogues; reactions attributable to the pharmacological effect of the drug), although other factors such as underlying disease, complications, concomitant drugs, or concurrent treatment are presumable. |
| Probable | An AE that follows a reasonable temporal sequence from administration of the drug (including the course after withdrawal of the drug) and that can be excluded as being possibly caused by other factors, such as underlying disease, complications, concomitant drugs, or concurrent treatment. |
| Definite | An AE that follows a reasonable temporal sequence from administration of the drug (including the course after withdrawal of the drug), follows a known or hypothesized cause–effect relationship, and (if appropriate) satisfies the following: 
• Positive results obtained in drug sensitivity tests• Toxic level of the drug present in blood or other body fluids |

8.5. Safety Monitoring

8.5.1. Data Safety Monitoring Board

The study will be performed under review by an external independent Data Safety and Monitoring Board (DSMB) to closely monitor the safety and welfare of the study subjects. The DSMB will be comprised of experienced hepatologists and other relevant specialists. The DSMB will review study data at regular intervals and determine whether it is safe to

continue the study according to the protocol. The DSMB members will be independent of the sponsor, the clinical study sites, and investigators. The event definitions information relevant to the operation of the committee will be described in a DSMB Charter.

8.5.2. Independent Adjudication

In addition to the DSMB, NGM will incorporate a formal Adjudication process for:
a) drug-induced liver injury (DILI) monitoring as part of the Liver Events Adjudication Committee, b) hepatocellular carcinoma (HCC), and c) cardiovascular events. Adjudication of possible/suspected cases will be conducted by independent clinicians with relevant clinical expertise. A cardiovascular adjudication committee is already in place across all aldafermin studies and performs blinded review of known and suspected cardiovascular events with focus on CV death, MI and hospitalization for heart failure and cerebrovascular accident (stroke). The Cardiovascular adjudication also reviews off-target effects of the potential investigational products on parameters potentially influencing the overall cardiovascular risk, such as: plasma lipids, glucose homeostasis, and (systemic) inflammatory (and fibrosis) parameters.

9. STATISTICAL CONSIDERATIONS

A detailed statistical analysis plan (SAP) will be provided and finalized prior to the study database lock or unblinding. No discrepancies are expected between the SAP and the protocol. However, if there are discrepancies between this section of the protocol and the final SAP, the SAP will override the protocol.

In general, descriptive statistics including the number of non-missing observations (n), arithmetic mean (mean), standard deviation (SD), median, minimum, and maximum will be presented for continuous variables, frequency and percentage distribution for categorical variables, and Kaplan–Meier estimates for time-to-event variables.

9.1. Sample Size Determination

The sample size for this study is determined based on power simulations for the modified primary efficacy endpoint (the change in ELF at Week 48) and using the analysis method described in [Klingenberg \(2009\)](#). Based on the ALPINE 2/3 study, the change from baseline in ELF at Month 6 (24 weeks) are 0.066, 0.083, -0.013, and 0.224 for placebo and aldafermin 0.3 mg, 1.0 mg, and 3.0 mg, respectively. Assuming a change in ELF of 0.1 for subjects treated with placebo, and a change in ELF of -0.4 at Month 12 (48 weeks) for subjects treated with aldafermin 3 mg, and a 15% subject drop-out rate at Week 48, a sample size of 150 subjects will provide at least 92% power to detect an upward dose-response trend at the 5% significance level (two-sided) ([Table 11](#)). Under protocol Version 5.0 and subsequent versions, eligible subjects will no longer be randomized into the 0.3 mg aldafermin treatment group. Instead, subjects will be randomized into 1 of 3 treatment groups in a 4:3:4 ratio to receive either subcutaneous placebo, 1 mg aldafermin or 3 mg aldafermin, respectively. Subjects randomized to the 0.3 mg aldafermin treatment group prior to protocol Version 5.0 will continue to receive the same dose until treatment completion. No more than 30% of the remaining population will be enrolled with the expanded Baveno VI criteria. The power under the new randomization is expected to be higher than that under the original randomization (3:2:2:3). More details of the power simulations will be provided in the SAP.

Based on the modified primary endpoint of the change from baseline in ELF at Week 48 and the analysis results from ALPINE 2/3, the following table presents the change from baseline needed for different powers.

Table 11. Power Simulations for the Primary Efficacy Analysis

| Assumed Change from Baseline in ELF at Week 48 | | Power |
|--|---------|--------|
| Aldafermin 3 mg | Placebo | |
| -0.224 | 0.066 | 51.00% |
| -0.3 | 0.066 | 69.83% |
| -0.3 | 0.1 | 77.33% |
| -0.4 | 0.066 | 88.35% |
| -0.4 | 0.1 | 92.33% |
| -0.5 | 0.1 | 99.25% |

9.2. Analysis Populations

Subjects will be analyzed using the following analysis populations:

- Intent to treat (ITT) population: all randomized subjects
- Modified ITT (mITT) population: all subjects who receive at least 2 weeks of study drug and have at least one valid, post-dose, on-treatment ELF score
- Safety population: all subjects who receive at least one dose (full or partial) of study drug
- Full-Analysis population: all randomized subjects who receive at least one dose (full or partial) of study drug and have at least one valid, non-missing post-dose efficacy/PD parameter value
- Per-Protocol (PP) population: a subset of subjects in the Full Analysis population who have valid, non-missing baseline and post-dose liver biopsy results and do not have protocol deviations that impact the liver biopsy assessments
- PK population: all randomized subjects who receive at least one dose (full or partial) of drug and have a qualified (i.e., above the lower limit of quantification) pre-dose and post-dose (at least one) PK assessment

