2.4. Mechanism of Action of Aldafermin

Aldafermin is 95.4% identical to FGF19. FGF19 and its murine homologue FGF15 have been implicated in the regulation of hepatic bile acid (BA) metabolism. FGF19 interacts with the FGFR4/ β -klotho receptor complex located in the liver to induce the expression of small heterodimer partner (SHP), an orphan nuclear receptor, in the liver to suppress the expression of *CYP7A1*, the gene encoding cholesterol 7 α -hydroxylase. In catalyzing the first, and rate-limiting step in the conversion of cholesterol into BAs, cholesterol 7 α -hydroxylase represents the key regulatory checkpoint in the control of BA synthesis, and changes in the level of this enzyme have been shown to have a significant effect on both the size and composition of the BA pool ([Russell 2003](#)). Additionally, FGF19 interacts with the FGFR1c/ β -klotho receptor complex located in the adipose tissue and the brain to regulate insulin sensitivity, glucose metabolism, and energy homeostasis ([Kliwer 2015](#)).

Aldafermin differs from wild-type FGF19 in the amino terminus, a key region of the protein involved in receptor interactions and signaling modulation ([Zhou 2014](#), [DePaoli 2019](#), [Luo 2014](#)). In aldafermin, a 5-amino acid deletion (P24-S28) coupled with the substitution of three amino acids at critical positions (A30S, G31S, H33L) enable biased FGFR4 signaling so that aldafermin retains the ability to potently repress CYP7A1 expression but no longer triggers activation of signal transducer and activator of transcription 3, a signaling pathway essential for FGF19-mediated hepatocarcinogenesis ([Zhou 2017](#)). By engaging both FGFR4 and FGFR1c pathways to reduce bile acid toxicity and lipotoxicity, and to improve insulin sensitivity, aldafermin has demonstrated robust anti-steatotic, anti-inflammatory, and anti-fibrotic activities in multiple animal models of NASH ([Zhou 2017](#), [Zhou 2019](#)).

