In the Phase 2 [Study 15-0105](#), the integrated safety data from the noncirrhotic NASH subjects double-blind and single-blind cohorts demonstrated a dose-dependent increase in the incidence of most commonly-occurring treatment-emergent adverse events (TEAEs), i.e., $\geq 10\%$, comprising gastrointestinal symptoms, headache, fatigue, and injection site erythema, with incidence plateauing from 1 mg (90%), 3 mg (86%), to 6 mg (86%). The 6 mg dose of aldafermin was associated with more drug-related treatment discontinuations and study withdrawals compared to the 3 mg dose, and hence was not further evaluated.

In addition, data from the double-blind cohort suggest that both the 3 and 6 mg doses of aldafermin have equivalent efficacy in terms of reductions in LFC, liver transaminases, and anti-fibrotic markers. The primary endpoint of $\geq 5\%$ decrease in absolute LFC was met in 57%, 90%, and 100% of the 0.3 mg, 1 mg, and 3 mg doses, respectively. Noninvasive marker analyses demonstrated a dose dependent and significant decrease in Pro-C3 and enhanced liver fibrosis (ELF) scores at these doses. ALT decreased rapidly and was similar for the 1 mg and 3 mg doses. The decrease in ALT levels was lesser in magnitude and plateaued above the ULN for most of the subjects in the 0.3 mg group. A total of 43 subjects were enrolled in the 1 and 3 mg single-blind dose cohorts and completed 12 weeks of treatment with paired biopsies. At Week 12, a greater proportion of subjects in the 3 mg arm (i.e., 68%) than 1 mg arm (i.e., 50%) met the histologic responder criteria.

These studies also showed that repeat dosing of aldafermin does not cause accumulation of aldafermin systemically due to the short (~5 hour) half-life. Additionally, NGM does not expect an increased risk of liver injury in well-compensated cirrhotic NASH subjects as aldafermin is not metabolized in the liver.

Therefore, based on the totality of the safety, tolerability, and efficacy data from these studies, NGM has selected aldafermin doses of 0.3, 1, and 3 mg for evaluation in this Phase 2b study. These selected doses are within the safety margins determined from the chronic toxicology studies in mice, rats, and monkeys.

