Up to approximately 150 eligible subjects will be randomized into 1 of 4 treatment groups in a 3:2:2:3 ratio to receive either subcutaneous placebo, 0.3 mg aldafermin, 1 mg aldafermin, or 3 mg aldafermin, respectively. Under protocol Version 5.0 and subsequent versions, eligible subjects will no longer be randomized into the 0.3 mg aldafermin treatment group. Instead, subjects will be randomized into 1 of 3 treatment groups in a 4:3:4 ratio to receive either subcutaneous placebo, 1 mg aldafermin or 3 mg aldafermin, respectively. Subjects randomized to the 0.3 mg aldafermin treatment group prior to protocol Version 5.0 will continue to receive the same dose until treatment completion. No more than 30% of the remaining population will be enrolled with the expanded Baveno VI criteria.

Randomization will be stratified by clinical diagnosis of T2D versus no T2D to ensure planned allocation ratio of treatment groups within each stratum (see [Table 6](#) [Version 1.0-4.0], [Table 7](#) [Version 5.0], and [Figure 2](#)).

Table 6. Study Design 282-CC-207 (Versions 1.0-4.0)

[figure not shown]
| Treatment Group | Dose of aldafermin (mg) | Mode of Treatment | Regimen | Number of Subjects Planned |
|-------------------------------|-------------------------|-------------------|---------|----------------------------|
| 1 | 0 (Placebo) | | | 45 |
| 2 | 0.3 | | | 30 |
| 3 | 1 | Subcutaneous | Daily | 30 |
| 4 | 3 | | | 45 |
| Total Subjects Planned | | | | 150 |

Table 7. Study Design 282-CC-207 (Version 5.0)

| Treatment Group | Dose of aldafermin (mg) | Mode of Treatment | Regimen | Number of Subjects Planned |
|-------------------------------|-------------------------|-------------------|---------|----------------------------|
| 1 | 0 (Placebo) | | | 52 |
| 2 | 0.3 | | | 8 |
| 3 | 1 | Subcutaneous | Daily | 38 |
| 4 | 3 | | | 52 |
| Total Subjects Planned | | | | 150 |

Figure 2. Schematic Overview of the Study Design

ALPINE 4 Trial Design & Patient Population

Study drug self-administration instructions and training will be provided to the subjects and study drug kits will be dispensed. Subjects will self-administer in the clinic the first dose of aldafermin/ placebo (Day 1) and doses at Weeks 2, 6, 12, 18, 24, 30, 36, 42, and 48 study visits. Subjects will self-administer all other doses through Week 48 at home.

Self-administration should occur at a similar time for every dose in both the clinic and at home.

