20. Consumption of ≥ 21 units of alcohol per week in males and ≥ 14 units of alcohol per week in females for two years prior to screening, where a "unit" of alcohol is equivalent to a 12-ounce beer, 4-ounce glass of wine, or 1-ounce shot of hard liquor.
21. Use of any prohibited concomitant medications as described in [Section 6.4](#) within 3 months prior to screening;
 - a. Weight loss medications.
 - b. Any medication that is contraindicated according to the rosuvastatin package insert ([Appendix 5](#)) or if subject has a known hypersensitivity to rosuvastatin product components ([Section 6.1.3](#)).
 - c. Hepatotoxic medications ([Appendix 6](#)); allopurinol allowed.
 - d. Anabolic steroids.
22. History of statin intolerance, as defined by presence of significant side effects while on statins and/or inability to take or use statins for treatment.
23. Prior participation in a clinical trial of aldafermin unless previously enrolled into a placebo arm of the trial.
24. History of severe allergic or anaphylactic reactions to recombinant therapeutic proteins, fusion proteins, or chimeric, human, or humanized antibodies.

25. Participation in a study of another investigational agent within 28 days or five half-lives of the drug (whichever is longer) prior to Screening.
26. Any acute or chronic condition that, in the opinion of the investigator, would limit the subject's ability to participate, complete, and/or would confound data interpretation in this clinical study.

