^[h] All subjects are required to have a liver biopsy result at Screening and additional liver biopsy at Week 48. A Screening liver biopsy will be performed only in subjects who do not have a qualified historical biopsy available for central pathology evaluation. The Week 48 biopsy should be obtained before the last dose of aldafermin with a visit window of 7 days prior to the end of treatment period.

^[i] Adverse events will be monitored and recorded from subject signing informed consent through follow-up.

^[j] Serum chemistry will include ALT, AST, ALP, bicarbonate, bilirubin (direct and total), BUN, calcium, chloride, creatinine, CK, GGT, glucose, HDL, LDL, phosphate, potassium, proteins (albumin, total protein), sodium, total cholesterol, and TG. Lab results for ALT, AST, total cholesterol, LDL, HDL, and triglycerides are blinded to the site and sponsor from Week 2 onward.

[k] Creatine kinase will be collected at all time points as serum chemistry.

[l] Per Exclusion #7, total bilirubin, AST, ALT, ALP

[m] A serum pregnancy test will be performed on all female subjects of childbearing potential at Day -56 Screening visit, Week 24, and Week 48. A urine pregnancy test will be performed on all female subjects of childbearing potential at all study visits through EOS.

[n] Urine drug and alcohol tests may be repeated during treatment for subjects suspected of excessive alcohol intake or to rule out association with a safety event.

[o] Serum bile acids will be collected pre-dose Day 1 and Week 48/early withdrawal.

[p] C4 will be collected pre-dose on Day 1 and Weeks 2, 6, 12, 18, 24, 30, 36, 42, 48 and 4-h post dose on Days 1, Weeks 24, and 48. In addition, for subjects participating in the optional PK sub-study, additional C4 will be tested at the same time points as the PK blood sample collections: Day 1 and Week 48 at pre-dose, and post-dose at 0.5, 1, 2, 4, 6, 8, 12, and 24 hours. The window for sample collection for the pre-dose through 4 hours is ± 5 minutes, 6-12-hour time points is ± 30 minutes. The window for sample collection for the 24-hour time points is -2 hours.

[q] PK blood samples will be collected in all subjects before dosing themselves in the clinic (pre-dose) on Day 1, Weeks 2, 6, 12, 18, 24, 30, 36, 42, and 48 and 4-hours post-dose on Day 1, Week 24 and Week 48.

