[r] For subjects participating in the optional PK sub-study, blood samples will be collected when the subjects dose themselves in the clinic on Day 1 and Week 48 at pre-dose, and post-dose at 0.5, 1, 2, 4, 6, 8, 12, and 24 hours. The window for sample collection for the pre-dose through 4 hours is ± 5 minutes, 6-12-hour time points is ± 30 minutes. The window for sample collection for the 24-hour time points is -2 hours.

[s] A single buccal swab sample for PNPLA3/other genetic biomarkers will be collected pre-dose on Day 1.

[t] Subjects will be instructed to self-inject aldafermin/placebo in the abdomen at a similar time each day. Subjects will not self-inject aldafermin/placebo at home on clinic visit day.

[u] Rosuvastatin will be dispensed at Weeks 2, 6, 12, 18, 24, 30, 36, and 42 visits and subjects will be provided further dosing instruction based on their ASCVD risk assessment, prior statin history (statin naïve or statin experienced), and LDL-C levels or LDL reduction levels. Subjects on a statin at Screening will switch from their current statin to an equivalent intensity dose of rosuvastatin at Week 2 and will be dispensed additional rosuvastatin at Week 48 and continue through Week 54 (or Week 58 if LDL-C follow-up is needed).

[v] For subjects who were statin experienced at Baseline, medication compliance will be assessed at Week 54 only.

[w] All subjects will be assessed at Weeks 49 and 54 to confirm their LDL-C levels are decreasing to near baseline, at which point, no additional follow-up is needed. Subjects who do not meet LDL-C decrease criteria at Week 54 will have an additional 4-week follow-up visit at Week 58 to confirm their LDL-C has returned to near baseline.

[x] ONLY for subjects who were identified at Week 49 as needing re-assessment of LDL-C at Week 54, the third-party Medical Monitor will evaluate LDL-C results to assess the need to schedule a 4-week LDL-C safety follow-up visit (Study Week 58) to confirm their LDL-C value has returned to near baseline.

[y] For EW patients only, the last, on-treatment ELF values at the visit prior to the EW visit will also be measured, in addition to the EW visit. This measurement will be done using the banked serum samples for the Exploratory Biomarker.

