8.2.12. Week 48 / Early Withdrawal (End of Treatment) Procedures

Subjects will report to this visit fasted and not dosed with aldafermin.

The following procedures will be performed at the Week 48/Early Withdrawal visit:

Pre-dose:

- Measure body weight, BMI, and waist circumference
- Conduct physical examination and RUQ pain assessment with NRS
- Obtain 12-lead ECG (after subject has been supine for at least 5 minutes)

- Measure vital signs (including temperature, respiratory rate, and seated blood pressure and pulse)
- Conduct Chronic Liver Disease Questionnaire for NASH (CLDQ-NASH)
- Obtain FibroScan® scores (for transient elastography, VCTE™ and steatosis by ultrasound attenuation rate CAP™), where available
- Obtain an ultrasound liver for routine HCC surveillance
- Undergo a liver biopsy procedure to obtain new tissue
- Record concomitant medications
- Record AEs
- Obtain 10-hour fasted clinical laboratory samples for the following:
 - Chemistry
 - CBC
 - HbA1c
 - [REDACTED]
 - Insulin level
 - HOMA-IR calculation
 - INR
 - AFP
 - Serum pregnancy test (all female subjects of childbearing potential)
 - Lipid panel
 - Lipoprotein particles
 - Lipase
 - C4
 - Serum bile acids
 - PK
 - ADAs
 - NAbs
 - ELF panel
 - Pro-C3
 - Pro-C3X
 - CTX-III
 - C3M
 - Exploratory Plasma biomarker #1

- Exploratory Plasma biomarker #2
- Exploratory Serum biomarker #3

Results for ALT, AST, Total Cholesterol, LDL, HDL, and triglycerides are blinded to the site and sponsor.

Obtain urine sample:

- Urinalysis
- Urine drug screen

In-clinic dosing:

- Collect old aldafermin study drug kit and diary and conduct reconciliation
- Collect old rosuvastatin bottle and diary and conduct reconciliation
- Re-dispense rosuvastatin study drug and diary (only for subjects who were statin experienced at Baseline). Remind Subjects that they will be contacted in a few days regarding the delivery or pick up of their rosuvastatin/placebo drug bottles.
- Oversee subject's aldafermin study drug self-administration (from old kit) (not applicable for Early Withdrawal subjects)
- Perform LISSA evaluation.
- Obtain PK blood sample 4-hours post dose.
- Obtain C4 blood sample 4-hours post dose

Before clinic discharge:

(NOTE: PK sampling before clinic discharge is not applicable for Early Withdrawal subjects; however, Early Withdrawal subjects should be scheduled for a 6-week Follow-up visit.)

- Schedule subject for Week 49 Post-Treatment Response Visit

Lipid Lowering Therapy Assessment:

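### The PK population requires a quantifiable pre-dose concentration at no named visit: Day 1 is drug-free and later pre-dose samples are about 24 h troughs, so entry is either nearly impossible or depends on measured exposure

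*Protocol*

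**What the plan says.** Protocol Section 9.2 defines the PK population as randomised subjects with at least one full or partial dose who "have a qualified (i.e., above the lower limit of quantification) pre-dose and post-dose (at least one) PK assessment". The synopsis uses the same words. Both samples must exceed the lower limit of quantification (LLOQ), and neither place says which visit's pre-dose sample counts.

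Other sections fix what a pre-dose sample can contain:

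- Section 8.1, Table 8, footnote q: "PK blood samples will be collected in all subjects before dosing themselves in the clinic (pre-dose) on Day 1", then at Weeks 2, 6, 12, 18, 24, 30, 36, 42 and 48. The 4 h post-dose samples are on Day 1 and at Weeks 24 and 48.
- Section 4.1: the first dose is given in clinic on Day 1, dosing is daily, and doses are taken at a similar time each day.
- Exclusion criterion 23 bars "Prior participation in a clinical trial of aldafermin unless previously enrolled into a placebo arm of the trial".
- Table 8, footnote t: "Subjects will not self-inject aldafermin/placebo at home on clinic visit day".
- Section 2.8: "repeat dosing of aldafermin does not cause accumulation of aldafermin systemically due to the short (~5 hour) half-life".
- Section 8.2.12 lists a pre-dose PK draw at the Week 48/Early Withdrawal visit but notes that "PK sampling before clinic discharge is not applicable for Early Withdrawal subjects".

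The visible text gives no LLOQ. The PK analysis text in the synopsis and Section 9.7 is redacted.

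**The concern.** Secondary endpoint 4 is the aldafermin concentration itself, pre-dose and 4 h post-dose. A population for summarising concentrations should not be chosen by how high those concentrations are. A trough below the limit is a valid result for a subject with low exposure. Under this rule, if all of a subject's troughs are below the limit, they remove the subject's quantifiable 4 h values as well. Those lost would be mainly subjects on the lowest dose and those who eliminate the drug fastest, so the remaining means would be too high and the comparison between doses distorted.

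The rule also sits badly with its own opening clause, which asks for only one full or partial dose. A subject who stops before Week 2 can have a valid Day 1 4 h sample. The only scheduled pre-dose draw after the first dose open to that subject is the one at the Early Withdrawal visit.

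**Working it through.** The plan states no figure to reproduce, so the check has two parts.

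**1. What each reading of pre-dose implies**

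*Day 1.* The first dose follows this sample and earlier aldafermin recipients are excluded, so it contains no study drug. Essentially nobody could properly qualify.

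*Weeks 2 to 48.* With daily dosing at a similar time and no home injection on visit days, the sample comes about 24 h after the last dose. Assume first-order decay, with t½ = 5 h from Section 2.8 and 4 to 6 h as an assumed range:

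- Fraction left at 24 h = 0.5^(24/t½). At 5 h this is 0.5^4.8 = 3.6% (1.6% at 4 h, 6.3% at 6 h).
- Accumulation ratio = 1/(1 − 0.5^(24/t½)). At 5 h this is 1.04, which agrees with the protocol's statement of no accumulation.
- Trough relative to the 4 h level = 0.5^(20/t½). At 5 h this is 0.5^4 = 6.25% (3.1% at 4 h, 9.9% at 6 h).
- The 4 h level must therefore be 1/0.0625 = 16 times the LLOQ before a typical trough is quantifiable (about 10 to 32 times over the assumed range).

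Under dose proportionality (assumed), typical troughs as a percentage of the median 3 mg 4 h level are 6.25 × 0.3/3 = 0.6% at 0.3 mg, 6.25 × 1/3 = 2.1% at 1 mg and 6.25% at 3 mg. As the LLOQ rises, the lowest dose is lost first.

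**2. Illustration of size**

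Inputs from the protocol: t½ of about 5 h, and 8, 38 and 52 planned subjects at 0.3, 1 and 3 mg (Table 7; 98 in all). Assumed inputs: dose proportionality, between-subject CV 50% in the 4 h level and 25% in half-life, within-subject CV 30% for troughs, and any one of the nine troughs sufficing.

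Model, with Z1 and Z2 standard normal:

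- C4h = (dose/3)·exp(0.472·Z1)
- t½ = 5·exp(0.246·Z2)
- best trough = C4h·2^(−20/t½)·exp(0.294·M), where M is the largest of nine standard normals
- a subject is kept if the best trough is at least the LLOQ
- bias = mean C4h of those kept / mean C4h of all − 1

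Results from 1,000,000 simulated subjects per dose, with the LLOQ as a percentage of the median 3 mg 4 h level:

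| LLOQ | Kept, 0.3/1/3 mg (%) | Bias, 0.3/1/3 mg (%) | Lost of 98 |
|---|---|---|---|
| 0.05% | 99.7/100/100 | 0.1/0/0 | about 0 |
| 0.5% | 76/97/99.7 | 9/1/0.1 | about 3 |
| 1% | 47/89/99 | 22/4/0.5 | about 9 |
| 2% | 17/70/95 | 48/11/2 | about 21 |

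Sensitivity at an LLOQ of 1%:

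- Median half-life 4 h or 6 h instead of 5 h: the 1 mg bias becomes 10.6% or 1.3%, against 3.9%.
- One given trough required instead of any of nine, keeping the 30% within-subject CV: 34/8/1%.
- CV of 30% instead of 50% in the 4 h level: 10/1/0.2%.

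**The case against.** The strongest reply is that no harm can be shown from this document. Size is driven by the LLOQ relative to the concentrations, which is not given, and with a sensitive assay the effect is nil. The CVs and dose proportionality are assumed. Decay from the 4 h sample after a subcutaneous injection is assumed to be simple first-order, and no Tmax is given. All of this stands, and it is why the figures above are illustration only.

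The largest figures belong to 0.3 mg, an arm closed to randomisation under Version 5.0 with 8 planned subjects: "Subjects randomized to the 0.3 mg aldafermin treatment group prior to protocol Version 5.0 will continue to receive the same dose until treatment completion". That stands too. A reader might infer that the 1 mg and 3 mg arms are therefore safe, with a bias of 4% or less. That holds only at an LLOQ of 1% or below and a half-life near 5 h.

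The redacted PK text may set its own rules by visit, and Section 9 lets the SAP override it. Which summaries use this population is therefore unknown. But the population rule is unredacted in both places, and Section 9 expects no discrepancies with the SAP, so the wording would probably carry over.

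Three stronger readings are tempting but unsupported:

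- From "Aldafermin is 95.4% identical to FGF19" in Section 2.4, a reader might infer that any Day 1 pre-dose signal is assay cross-reactivity with endogenous FGF19. That sentence gives sequence identity; the documents say nothing about assay specificity, and contamination or a sample mix-up would also give a signal.
- A reader might infer that early stoppers are always lost. The protocol gives no interval between last dose and the Early Withdrawal visit, and no number stopping before Week 2.
- A reader might infer that the trial's efficacy or safety conclusions are at risk. The efficacy analyses use ITT, with other efficacy populations as sensitivity analyses, and safety uses the Safety population.

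**Conclusion.** The point holds as a minor defect in a rule that the protocol states in full. Read for Day 1, the PK population is essentially empty. Read for later visits, entry is selected on the measured endpoint. The direction on the second reading is clear: summaries of concentration made in this population are biased upward, most at the lowest dose. The size is not determinable from the protocol. The illustrated range at 0.3/1/3 mg runs from nil (LLOQ 0.05% of the median 3 mg 4 h level) through 22/4/0.5% (1%) to 48/11/2% (2%), and it depends on the assumed half-life, CVs and dose proportionality. Any consequence is confined to PK summaries that use this population. All samples are still collected, so it can be corrected without loss before database lock.

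**What to change.** In Section 9.2 and the synopsis, define the PK population as all randomised subjects who received at least one dose (full or partial) of aldafermin and have at least one reportable concentration result, including results below the LLOQ, from any sample taken after the first dose. State that troughs labelled pre-dose count. The protocol uses pre-dose and 4 h post-dose as separate labels, so asking only for a post-dose sample would leave it unclear whether a subject with troughs but no 4 h draw is included. Delete the requirement for a pre-dose value above the LLOQ.

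The cost is one sentence in two places. It needs no new samples, no change to visits and no knowledge of the LLOQ.
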